### **6.13.6. Electrocardiograms**

ECG measurements will be analyzed using continuous data (change from baseline) and categorical data (proportion of treatment-emergent abnormalities) using the Safety Dataset.

The ECG measurements are derived from three 10 second readings taken every 30 seconds. These 3 readings are to be averaged prior to analysis. Additionally, whenever ECG is measured in triplicate, the average of these readings will be used in the analysis. If there are multiple records after averaging ECG triplicates within a visit, the last record of averages will be used.

The analysis will be done for the following ECG measurements: heart rate, PR, QT, QTc, and RR intervals and QRS duration. All analyses of QTc will be carried out using the Fridericia correction (QTcF) method. Measures of central tendency for ECG raw measurements and change from baseline will be summarized with boxplots. Boxplots will display results semi-annually (visits 8, 15, 22, and 28) and for the last visit (LOCF) and will include summary tables of N, mean, median, quartiles, min, max, standard deviation, and p-value (for change scores). If there are considerable missing visits, the measures of central tendency may be based on MMRM analyses.

In order to assess outliers and potentially clinically significant changes from baseline, the number and percent of patients meeting criteria for treatment-emergent abnormalities in ECGs will be summarized. Treatment group comparisons will be performed using Fisher's exact test. Baseline is defined as the entire screening period (visits 1 and 2), and all baseline assessments must not meet abnormality criteria to be included in the analysis. Incidence of treatment-emergent abnormal ECGs will be assessed by comparisons at (1) anytime and (2) semi-annually (visits 8, 15, 22, and 28).

Abnormal ECG criteria and criteria for abnormal QTcF prolongation are presented in [Appendix 2](#).

Treatment-emergent high ECG parameters (heart rate, PR interval, QRS duration, QT and QTcF intervals) are the values which are low or normal at all baseline visits and fall into the high abnormal categories post-baseline. Similarly, treatment-emergent low ECG parameters (heart rate, PR interval, QRS duration) are the values which are high or normal at all baseline visits and fall into the low abnormal categories above.

In addition, treatment differences in the proportion of patients who have normal baselines with a change to abnormal high or abnormal low values at any post-baseline visits will be summarized.

#### **6.13.7. Safety MRIs**

To evaluate white matter changes over time, a shift table will be created from the following categories:

- 0 = No lesions
- 1 = Focal lesions
- 2 = Beginning confluence of lesions
- 3 = Diffuse involvement of entire region

A listing of MRI data will also be presented.

#### **6.13.8. Immunogenicity**

The frequency and percentage of subjects with preexisting (baseline) ADA, ADA at any time after baseline, and TE-ADAs to LY3303560 will be summarized. If no ADAs are detected at baseline, TE-ADAs are defined as those with a titer 2-fold (1 dilution) greater than the MRD of the assay. For samples with ADA detected at baseline, TE-ADA are defined as those with a 4-fold (2 dilutions) increase in titer compared to baseline. For the TE-ADA subjects, the

distribution of maximum titers will be summarized. The frequency of subjects with neutralizing antibodies (subset of the TE-ADA patients) will also be summarized.

### **6.13.9. *Columbia Suicide Severity Rating Scale***

Suicidal ideation, suicidal behavior, and self-injurious behavior without suicidal intent occurring during treatment, based on the Columbia-Suicide Severity Rating Scale (C-SSRS), will be summarized by treatment. In particular, for each of the following events, the number and percent of patients with the event will be enumerated by treatment: completed suicide, nonfatal suicide attempt, interrupted attempt, aborted attempt, preparatory acts or behavior, active suicidal ideation with specific plan and intent, active suicidal ideation with some intent to act without specific plan, active suicidal ideation with any methods (no plan) without intent to act, nonspecific active suicidal thoughts, wish to be dead, and self-injurious behavior without suicidal intent. Although not suicide-related, the number and percent of patients with non-suicidal self-injurious behavior occurring during the treatment period will also be summarized by treatment.

In addition, the number and percent of patients who experienced at least one of various composite measures during treatment will be presented and compared. These include suicidal behavior (completed suicide, non-fatal suicidal attempts, interrupted attempts, aborted attempts, and preparatory acts or behavior), suicidal ideation [active suicidal ideation with specific plan and intent, active suicidal ideation with some intent to act without specific plan, active suicidal ideation with any methods (no plan) without intent to act, non-specific active suicidal thoughts, and wish to be dead], and suicidal ideation or behavior.

The number and percent of patients who experienced at least one of various comparative measures during treatment will be presented and compared. These include treatment-emergent suicidal ideation compared to recent history, treatment-emergent serious suicidal ideation compared to recent history, emergence of serious suicidal ideation compared to recent history, improvement in suicidal ideation at endpoint compared to baseline, and emergence of suicidal behavior compared to all prior history.

Specifically, the following outcomes are C-SSRS categories and have binary responses (yes/no). The categories have been re-ordered from the actual scale to facilitate the definitions of the composite and comparative endpoints, and to enable clarity in the presentation of the results.

Category 1 – Wish to be Dead

Category 2 – Non-specific Active Suicidal Thoughts

Category 3 – Active Suicidal Ideation with Any Methods (Not Plan) without Intent to Act

Category 4 – Active Suicidal Ideation with Some Intent to Act, without Specific Plan

Category 5 – Active Suicidal Ideation with Specific Plan and Intent

Category 6 – Preparatory Acts or Behavior

Category 7 – Aborted Attempt

Category 8 – Interrupted Attempt

Category 9 – Actual Attempt (non-fatal)

Category 10 – Completed Suicide

Self-injurious behavior without suicidal intent is also a C-SSRS outcome (although not suicide-related) and has a binary response (yes/no).

Composite endpoints based on the above categories are defined below.

- Suicidal ideation: A “yes” answer at any time during treatment to any one of the five suicidal ideation questions (Categories 1-5) on the C-SSRS.
- Suicidal behavior: A “yes” answer at any time during treatment to any one of the five suicidal behavior questions (Categories 6-10) on the C-SSRS.
- Suicidal ideation or behavior: A “yes” answer at any time during treatment to any one of the ten suicidal ideation and behavior questions (Categories 1-10) on the C-SSRS.

The following outcome is a numerical score derived from the C-SSRS categories. The score is created at each assessment for each patient and is used for determining treatment emergence.

- Suicidal Ideation Score: The maximum suicidal ideation category (1-5 on the C-SSRS) present at the assessment. Assign a score of 0 if no ideation is present.

Comparative endpoints of interest are defined below. “Treatment emergence” is used for outcomes that include events that first emerge or worsen. “Emergence” is used for outcomes that include events that first emerge.

- Treatment-emergent suicidal ideation compared to recent history:  
An increase in the maximum suicidal ideation score during treatment (Visits Y1-Y2) from the maximum suicidal ideation category during the screening and lead-in periods (C-SSRS scales taken at Visits X1-X2). Recent history excludes “lifetime” scores from the Baseline C-SSRS scale or Baseline/Screening C-SSRS scale.
- Treatment-emergent serious suicidal ideation compared to recent history: An increase in the maximum suicidal ideation score to 4 or 5 on the C-SSRS during treatment (Visits Y1-Y2) from not having serious suicidal ideation (scores of 0-3) during the screening and lead-in periods (C-SSRS scales taken at Visits X1-X2). Recent history excludes “lifetime” scores from the Baseline C-SSRS scale or Baseline/Screening C-SSRS scale.
- Emergence of serious suicidal ideation compared to recent history:  
An increase in the maximum suicidal ideation score to 4 or 5 on the C-SSRS during treatment (Visits Y1-Y2) from no suicidal ideation (scores of 0) during the screening and lead-in periods (C-SSRS scales taken at Visits X1-X2). Recent history excludes “lifetime” scores from the Baseline C-SSRS scale or Baseline/Screening C-SSRS scale.
- Improvement in suicidal ideation at endpoint compared to baseline:  
A decrease in suicidal ideation score at endpoint (the last measurement during treatment; Visits Y1-Y2) from the baseline measurement (the measurement taken just prior to treatment; (Visit X2). This analysis should only be performed for a non-lifetime baseline measurement (i.e., having improvement from the worse event over a lifetime is not clinically meaningful). A specific point in time can be used instead of endpoint.
- Emergence of suicidal behavior compared to all prior history:

The occurrence of suicidal behavior (Categories 6-10) during treatment (Visits Y1-Y2) from not having suicidal behavior (Categories 6-10) prior to treatment (Visits X1-X2). Prior to treatment includes “lifetime” and/or “screening” scores from the Baseline C-SSRS scale, Screening C-SSRS scale, or Baseline/Screening C-SSRS scale, and any “Since Last Visit” from the Since Last Visit C-SSRS scales taken prior to treatment.

Patients who discontinued from the study with no postbaseline C-SSRS value will be considered unevaluable for analyses of suicide-related events. Only evaluable patients will be considered in the analyses. Fisher’s exact test will be used for treatment comparisons.

## 6.14. Subgroup Analyses

To assess the effects of various demographic and baseline characteristics on treatment outcome, subgroup analyses for the primary endpoint, iADRS:

- APOE4 Carrier Status – Carrier defined as E2/E4, E3/E4, or E4/E4 genotype; No-Carrier defined as all other genotypes
- Disease status at baseline based on MMSE total score
  - MCI or mild AD (MCI: 27-30; mild AD: 20-26)
  - Grouped into thirds
- Tau burden at baseline based on eligibility tau PET SUVR
  - very low tau:  $SUVR < 1.10$ ; low tau:  $1.10 \leq SUVR < 1.23$ ; medium tau:  $1.23 \leq SUVR < 1.46$
  - Grouped into thirds

The primary outcome measure will be modeled using a DPM approach. This general model will include terms for baseline, treatment, pooled site, visit, concomitant AChEI/memantine use at baseline (yes/no), baseline age, treatment by visit, subgroup by treatment, subgroup by visit, and treatment by visit by subgroup. Redundant terms will be dropped from the model in those cases where the subgroup of interest is overlapping with this general model. In order to run these analyses, at least 20 patients are required in each strata-treatment combination.

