## 5. Study Design

### 5.1. Summary of Study Design

Study LMDC is a multicenter, randomized, double-blind, placebo-controlled, Phase 2 study of LY3303560 in patients with early symptomatic AD and low-to-medium cerebral tau burden. A combination of visual and quantitative assessments of tau PET is used to identify eligible patients:

- Visual assessment of AD+ (increased activity in posterior temporal regions only) AND  $1.10 < \text{SUVR} \leq 1.46$
- Visual assessment of AD++ (increased activity in temporal and parietal regions) AND  $\text{SUVR} \leq 1.46$

The maximum possible duration of the study is 121 weeks that includes a screening period of up to 8 weeks, a treatment period of 100 weeks, a 4-week post last dose assessment, and an immunogenicity and safety follow-up period of up to 13 weeks, following the last dose of the study drug at Week 100. Subjects who meet entry criteria will be randomized in a 1:1:1 ratio to one of the following treatments:

- **1400 mg LY3303560:** LY3303560 1400 mg IV infusion Q4W for 100 weeks (Visit 2 [Week 0] to Visit 27 [Week 100]).
- **5600 mg LY3303560:** LY3303560 5600 mg IV infusion Q4W for 100 weeks (Visit 2 [Week 0] to Visit 27 [Week 100]).
- **Placebo:** IV placebo infusion Q4W for 100 weeks (Visit 2 [Week 0] to Visit 27 [Week 100]).

The first safety review by a Data Monitoring Committee will be conducted after approximately 30 patients have received 3 doses and completed the 4 week assessment period ( i.e. just prior to their 4th dose). Enrolment will halt after these patients have received one dose of study treatment, however those patients already dosed will continue their allocated treatment. If any of these patients discontinue from study treatment for reasons other than safety, they may be replaced, upon discussion between the investigators and Lilly.

The primary hypothesis being tested is that LY3303560 administered for 100 weeks will result in a significant slowing in cognitive/functional decline compared with placebo as measured by the change from baseline to the end of the double-blind period (Week 104) on the integrated Alzheimer's Disease Rating Scale (iADRS), in subjects with early symptomatic AD (where early symptomatic AD refers to the combination of 2 stages: prodromal AD [mild cognitive impairment (MCI)-AD] and mild dementia due to AD; Alaka et al. 2015) who have low-to-medium tau burden.

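### By eligibility the 'very low tau' class holds only AD++ patients, so contrasts of treatment effect between it and the other SUVR classes confound tau level with visual pattern

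*SAP*

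**What the plan says.** Section 5.1 gives two routes into the trial. The first is "Visual assessment of AD+ (increased activity in posterior temporal regions only) AND" an SUVR above 1.10 and no higher than 1.46. The second is "Visual assessment of AD++ (increased activity in temporal and parietal regions) AND" an SUVR no higher than 1.46, with no lower limit.

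Section 6.14 defines the tau subgroup from SUVR alone: "Tau burden at baseline based on eligibility tau PET SUVR". The classes are very low (below 1.10), low (1.10 to below 1.23) and medium (1.23 to below 1.46). A second version is "Grouped into thirds", which the Revision History lists as added in version 6.

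The subgroup model contains baseline, treatment, pooled site and visit, followed by "concomitant AChEI/memantine use at baseline (yes/no), baseline age, treatment by visit, subgroup by treatment, subgroup by visit, and treatment by visit by subgroup". The analysis is run only if "at least 20 patients are required in each strata-treatment combination". The visual read is neither a model term nor a subgroup, and no analysis restricted to one visual pattern is planned.

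**The concern.** Section 6.14 exists to show whether the treatment effect varies with baseline characteristics. For tau, the informative quantity is therefore the contrast of treatment effect between SUVR classes. The eligibility rule makes the lowest class differ from the others in two respects at once: it has less tracer signal, and it contains nobody with the more limited, posterior temporal pattern.

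If the disease progression ratio (DPR) in the very low class differs from that in the low or medium class, the planned output cannot say which of the two is responsible. The label adds to the difficulty, because the class named for the least tau consists entirely of patients with the more widespread visual pattern. Tau burden defines this trial's population, so the result could well be used when choosing patients for a later study.

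**Working it through.** **1. Eligible cells.** Applying the Section 5.1 rules and then the Section 6.14 cut-points, on an SUVR grid of 0.01, gives:

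| Class (6.14) | AD+ eligible | AD++ eligible |
|---|---|---|
| very low, below 1.10 | none | up to 1.09 |
| low, 1.10 to <1.23 | 1.11 to 1.22 | 1.10 to 1.22 |
| medium, 1.23 to <1.46 | 1.23 to 1.45 | 1.23 to 1.45 |

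The very low by AD+ cell is empty by design. The low and medium classes can hold both patterns, though their mix may differ. In the thirds version, the lowest third is wholly AD++ if its upper cut lies at or below 1.10. It is partly enriched for AD++ if the cut lies higher but the third still includes patients below 1.10.

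**2. What a model can separate.** For three classes and three arms:

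- Class by treatment, as planned: 9 columns, rank 9.
- Adding visual read and visual read by treatment: 12 columns, rank 12. This is estimable, but only by assuming that the effect of visual pattern is the same at every SUVR level and carrying it into the empty cell.
- Adding visual read by class by treatment: 18 columns, rank 15. The three missing dimensions are the very low by AD+ cells in the three arms.

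**3. Illustrative size.** The SAP gives neither the AD+/AD++ split nor any pattern-specific effect, so these inputs are assumptions. Let q be the AD+ share in the comparison class and d the difference in slowing between AD+ and AD++. Suppose SUVR itself modifies nothing and placebo decline is the same in both patterns. The apparent difference in slowing between very low and that class is then q × d. On the 19.56-point placebo decline in Section 5.2, it amounts to 19.56 × q × d iADRS points:

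| q | d = 10 points | d = 25 points | d = 50 points |
|---|---|---|---|
| 20% | 2% (0.4 iADRS points) | 5% (1.0) | 10% (2.0) |
| 50% | 5% (1.0) | 12.5% (2.4) | 25% (4.9) |
| 80% | 8% (1.6) | 20% (3.9) | 40% (7.8) |

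If d = 0, the whole table is zero.

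**4. Against sampling error.** Section 5.2 gives a Week 104 SD of 20.9. At the minimum of 20 per cell, the standard error (SE) of a difference between two classes' treatment effects is 20.9 × √(4/20) ≈ 9.3 points. With 50 per arm in the larger class it is 20.9 × √(2/20 + 2/50) ≈ 7.8. Take d = 33% (the slowing assumed for 1400 mg in Section 5.2, here assigned to AD+ only) and q = 40% to 70%. The apparent gap is 0.13 to 0.23 in DPR, or about 2.6 to 4.5 points, which is roughly 0.3 to 0.6 SE. The DPM uses all visits, so its true standard error would be smaller than this Week 104 approximation.

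**5. Whether the analyses can run.** Twenty per arm in the very low class is 20/75 = 26.7% of each arm if N is 225 (title page), or 20/120 = 16.7% if N is 360 (Section 5.2). An AD++-only comparison over three classes and three arms needs 9 × 20 = 180 AD++ patients. If AD++ makes up 30–60% of low and 60–90% of medium (assumed), each arm needs between 20 + 20/0.6 + 20/0.9 ≈ 76 and 20 + 20/0.3 + 20/0.6 = 120 patients. That is about 227 to 360 in total, even with ideally sized classes.

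**The case against.** The SAP says openly that the subgroup rests on SUVR and does not claim to isolate tau amount from its distribution. Subgroup factors always carry other baseline features with them: the MMSE and APOE4 subgroups in the same section are not adjusted for tau either. The subgroup analyses lie outside the gated tests, and no decision rule in this SAP depends on them. The three-class version may not even meet the 20-per-cell rule. Section 6.1 allows further exploratory analyses, and Section 6.8 summarises tau PET burden at baseline.

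Most of this stands and limits the weight of the point. It does not remove it. Ordinary correlation between baseline factors leaves overlap from which they can be separated; here the eligibility rule empties one cell. Section 6.8 is descriptive only, and the general allowance in Section 6.1 does not name the visual read.

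A reader might infer that the whole tau subgroup analysis is biased. The documents do not support that. The treatment comparison within each class is still randomised, visual pattern is constant within the very low class, and the low versus medium contrast has no empty cell. A reader might also take the gaps illustrated in the working as estimates. They are not: every input on pattern split and pattern-specific effect is assumed, and gaps of the Section 5.2-anchored size would be well within sampling error at the minimum cell size.

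**Conclusion.** The point holds in a limited form. By the rules in Section 5.1, the very low tau class in Section 6.14 is AD++ only, apart from any patients enrolled in violation of eligibility. Contrasts of treatment effect between that class and the others confound SUVR level with visual pattern, as do contrasts between thirds if the lowest third reaches below 1.10. Nothing planned can separate the two.

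This first conclusion is set logic and needs no assumption beyond adherence to eligibility. The size of any distortion cannot be derived from the SAP and is zero if AD+ and AD++ patients respond alike. Comparisons with placebo within each class and the primary conclusion are untouched. This is a worthwhile, inexpensive improvement to an exploratory analysis and does not threaten the trial's main inference.

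**What to change.** In Section 6.14:

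- Add the screening visual read (AD+ versus AD++) as a two-level subgroup, under the same 20-per-cell rule.
- Repeat the SUVR comparison within AD++ patients only, as a supportive analysis. AD++ is the one pattern eligible at every SUVR level, so no extrapolation is needed. Use SUVR as a continuous variable, or merge classes, if cells fall below 20.
- State in the definition and in the outputs that very low tau consists of AD++ patients only, and report how many patients in the lowest third have SUVR below 1.10.
- Do not rely on a visual-read-by-treatment covariate alone, because it separates the two factors only by extrapolating into the empty cell.

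The cost is a few lines of SAP text and a few more exploratory runs on a read already made for eligibility. The AD++-only comparison will have clearly wider intervals, and in its three-class form it may not meet the minimum cell size.

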# 1. Statistical Analysis Plan: I8G-MC-LMDC: Assessment of Safety, Tolerability, and Efficacy of LY3303560 in Early Symptomatic Alzheimer's Disease

## Confidential Information

The information contained in this document is confidential and the information contained within it may not be reproduced or otherwise disseminated without the approval of Eli Lilly and Company or its subsidiaries.

**Note to Regulatory Authorities:** This document may contain protected personal data and/or commercially confidential information exempt from public disclosure. Eli Lilly and Company requests consultation regarding release/redaction prior to any public release. In the United States, this document is subject to Freedom of Information Act (FOIA) Exemption 4 and may not be reproduced or otherwise disseminated without the written approval of Eli Lilly and Company or its subsidiaries.

LY3303560

Alzheimer's disease

Multicenter, randomized double-blind, placebo-controlled, Phase 2 study comparing up to 5600 mg of LY3303560 with placebo over 104 weeks in approximately 225 patients with early symptomatic AD.

Eli Lilly and Company  
Indianapolis, Indiana USA 46285  
Protocol I8G-MC-LMDC  
Phase 2

SAP electronically signed and approved by Lilly on date provided below:

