### 3. Revision History

SAP Version 1 was approved on Oct. 10, 2018 prior to unblinding. SAP Version 2 was approved on Nov. 19, 2019 prior to efficacy unblinding. SAP version 3 was approved on Aug. 11, 2020 prior to interim analysis 2. SAP version 4 was approved April 21, 2021 prior to interim analysis 3. SAP version 5 was approved August 31, 2021 prior to the primary outcome lock. SAP version 6 was approved prior to the primary outcome lock and included the following changes:

- Fixed typo in description of number of missing items allowed in the ADAS-Cog13 scale (sec. 6.3)
- Added the Bayesian DPM thresholds for the Multiplicity Graph for iADRS LY5600 vs. placebo and iADRS LY1400 vs. placebo and a description calculating all of the thresholds included in the Multiplicity Graph (sec. 6.11.2)
- Updated ECG timepoints (sec. 6.13.6)
- Added two subgroup analyses: baseline tau grouped into thirds and baseline MMSE grouped into thirds, and updated subgroup definitions of disease severity based on MMSE (sec. 6.14)

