### 5.2. Determination of Sample Size

Based on the Disease Progression Model (DPM), 360 enrolled patients, a 30% dropout rate, and a 3-month delay of treatment effect onset, this sample size will provide more than 95% power to

demonstrate that at least one of the active treatment arms has slowed cognitive/functional decline. This claim of slowing cognitive/functional decline is based on showing that at least one of the active treatment arms has a  $\geq 0.6$  posterior probability of slowing of iADRS progression over placebo by at least 4 points (that is, 25% slowing relative to placebo, based on a mean change from baseline in the placebo group of 16 points and mean change from baseline on at least one of the active treatment arms of at most 12 points) after 104 weeks (approximately 24 months) on study treatment. This power calculation comes from simulations using a placebo decline of 19.56 points and 33% slowing on 1400 mg LY3303560 and 50% slowing on 5600 mg LY3303560 relative to placebo at 104 weeks. The variance-covariance matrix in the simulations had a variance at Week 104 of 436.85 (equal to a standard deviation of 20.9). If both active treatment arms are placebo-like with no efficacy, the probability of passing the efficacy criterion specified above (that is, false positive) is approximately 2.5%. To test the hypothesis of a disease progression benefit, we calculate the posterior probability of superiority in cognitive/functional slowing, and if it is above a pre-specified threshold (which controls the experiment-wise type I error at approximately 2.5%), then a claim of cognitive slowing will be made. The simulation for the power calculation and sample size determination was carried out in FACTS Version 5.5.

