### 5.3. Method of Assignment to Treatment

Patients who meet all criteria for enrollment will be assigned a study (patient) number at Visit 1 and randomized to double-blind treatment at Visit 2. Patients will be randomized to LY3303560 or Placebo in a 1:1:1 ratio. Assignment to treatment groups will be determined by a computer-generated random sequence using an interactive web response system (IWRS). For the first, approximately, 30 patients, the IWRS will be programmed to guarantee balance between the arms for the first interim analysis for safety; this is referred to as the burn-in period. After the burn-in period, patient randomization will then follow the dynamic allocation (minimization) method of Pocock and Simon (1975) to balance the treatment arms using investigative site as a factor. This is to ensure balanced patient assignment between treatment arms within each site at the end of the study.

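### The 20-per-cell condition in SAP 6.14 has no fallback, so one short cell can cancel the three-level tau subgroup analysis; the medium tau level also leaves out SUVR of exactly 1.46

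*SAP*

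**What the plan says.** Section 6.14 lists subgroup analyses of iADRS by APOE4 carrier status, by MMSE (MCI versus mild AD, and thirds) and by tau. The tau item, "Tau burden at baseline based on eligibility tau PET SUVR", has two groupings: three levels with fixed cut-points (very low, SUVR below 1.10; low, from 1.10 to below 1.23; medium, from 1.23 to below 1.46) and, separately, thirds. The section closes with the condition for running them: "at least 20 patients are required in each strata-treatment combination". It gives no alternative if the condition is not met.

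The thirds are recent. Section 3 records for version 6: "Added two subgroup analyses: baseline tau grouped into thirds and baseline MMSE grouped into thirds".

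These parts of the SAP bear on the cell counts:

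- Section 5.1, arms: "Subjects who meet entry criteria will be randomized in a 1:1:1 ratio", with three arms.
- Section 5.3, allocation: after the burn-in period it works "to balance the treatment arms using investigative site as a factor". Tau and MMSE are not balancing factors.
- Section 5.1, eligibility: the category "Visual assessment of AD+ (increased activity in posterior temporal regions only") must have an SUVR above 1.10 and no higher than 1.46. AD++ scans need only an SUVR no higher than 1.46.
- Sample size: the title page describes a trial "in approximately 225 patients with early symptomatic AD", while section 5.2 rests on "360 enrolled patients, a 30% dropout rate".

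**The concern.** A minimum cell size is sensible for a model that carries a treatment-by-visit-by-subgroup term. The weakness is that the consequence of missing it is cancellation, with nothing prespecified in its place. Read literally, one short cell in the very low tau level also removes the low-versus-medium comparison, even where those two levels hold enough patients.

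The very low level is the exposed one, because AD+ scans cannot enter it. The trial population is defined by low-to-medium tau, so this is a subgroup result that readers will look for. If the analysis is cancelled, any regrouping would be chosen after the fact, possibly with unblinded data in view.

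A second, smaller defect lies in the same list. Eligibility includes an SUVR of 1.46, but the medium level stops just short of it.

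**Working it through.** The SAP states no expected cell counts and no probability of meeting the condition, so there is no figure of its own to reproduce.

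**Inputs.** Minimum of 20 per cell (6.14); three arms at 1:1:1 (5.1); N = 225 (title page) or N = 360 (5.2); allocation balanced on site only (5.3). The share of patients with SUVR below 1.10 is not in the SAP and is treated as an assumption.

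**Floor per level.** 20 × 3 arms = 60 patients.

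- At 225: 60 / 225 = 26.7%.
- At 360: 60 / 360 = 16.7%.

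The floor is necessary but not sufficient. A level of exactly 60 passes only if it splits 20/20/20.

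**Chance that some cell is below 20.** Hold the arm totals and level totals fixed and take tau as independent of arm. A 3 × 3 table then has probability (product of row factorials × product of column factorials) / (N! × product of cell factorials). Sum this over all tables with every cell at least 20, and subtract the sum from 1.

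*Three-level tau, N = 360 (120 per arm), other two levels about equal:*

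| Assumed very low share | Patients | Chance of cancellation |
|---|---|---|
| 15% | 54 | 100% (below 60) |
| 20% | 72 | 31% |
| 22.5% | 81 | 6% |
| 25% | 90 | 1% |

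*Three-level tau, N = 225 (75 per arm), other two levels about equal:*

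| Very low patients | Share | Chance of cancellation |
|---|---|---|
| 45 | 20% | 100% (below 60) |
| 60 | 26.7% | 98% |
| 65 | 28.9% | 71% |
| 70 | 31.1% | 43% |
| 75 | 33.3% | 34% |

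*Thirds:*

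| N | Thirds | Mean per cell | Chance for each analysis |
|---|---|---|---|
| 225 | 75/75/75 | 225 / 9 = 25 | 34% |
| 225 | 70/75/80 | 25 | 44% |
| 225 | 65/75/85 | 25 | 73% |
| 216 | 72/72/72 | 24 | 51% |
| 360 | 120/120/120 | 40 | about 0.0002% |

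At 225 the 34% is close to a best case. MMSE is an integer score, so ties make its thirds unequal. Patients without a post-baseline iADRS also drop out of the Evaluable Efficacy population (Table 6.6.1).

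**The 1.46 boundary.** Section 5.1 admits SUVR ≤ 1.46 in both visual categories. Section 6.14 ends medium tau at SUVR < 1.46. A patient at exactly 1.46 is eligible and belongs to none of the three levels. This needs no assumption. How many such patients there are is unknown, probably very few, and the thirds would still include them.

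**The case against.** The strongest reply has four parts.

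- **Two sample sizes.** The tertile risk exists only at the title-page figure. A reader might infer that the tertile analyses fail about one time in three. The SAP does not support that as a general statement, because section 5.2 gives 360 and at that size the risk vanishes. This part of the reply stands.
- **Assumed shares.** The three-level percentages depend on a very low share that the SAP does not report. At 360, a share of 25% or more makes cancellation unlikely. That stands too; only the 60-per-level floor is free of assumption. That the very low level is the likeliest to fall short is an inference from the eligibility wording, with no count of AD++ scans behind it.
- **Other routes to a tau result.** A reader might infer that the report could end with no iADRS result by tau. For that, both the fixed-level and the tertile analyses would have to be cancelled. Section 6.1 also allows further exploratory analyses, so a merged-level summary is not barred. It is only not prespecified.
- **Timing and status.** Section 6.1.1 says enrolment was complete by March 2020, well before version 6, so the level totals were already settled and only their split by arm was unknown under blinding. These analyses are outside the multiplicity graph of section 6.11.2, and a minimum cell size is an ordinary safeguard.

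None of this supplies a rule for a short cell or closes the gap at 1.46. The timing argument in fact favours the change, since pooled level sizes could be checked without unblinding.

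**Conclusion.** The point holds as a minor one. Section 6.14 ties each subgroup analysis to 20 patients in every cell and does not say what follows if one is short. For the three-level tau analysis this means at least 60 patients in each level, and comfortably more than 60 for the analysis to be likely to run. Whether it would be cancelled depends on an unreported share: at 360 patients, cancellation ranges from certain at 15% to about 1% at 25%; at 225 it is certain at 20% or less.

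The tertile concern applies only if the trial size is about 225, and the SAP leaves 225 and 360 unreconciled. The probabilities assume equal arms, fixed level totals and tau or MMSE independent of arm. The omission of 1.46 is certain but probably touches very few patients. The primary iADRS test does not depend on any of this.

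**What to change.** In section 6.14:

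1. Keep the minimum of 20 per cell, and add that when any cell falls short, adjacent levels are merged and the analysis is run on the merged levels: very low with low tau, and thirds replaced by halves split at the median.
2. Define medium tau as 1.23 ≤ SUVR ≤ 1.46.

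Elsewhere, reconcile the 225 on the title page with the 360 in section 5.2, so that a reader can tell which groupings are at risk.

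The cost is a few sentences of SAP text and no new data. The downside is that merged levels are coarser, so an effect confined to the very low tau level could no longer be seen separately.
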